### 9.3. Secondary Outcomes

In addition to a full description of the populations in each group throughout the trial, the following outcomes will be measured:

- cardiac function assessed by echocardiogram, including global longitudinal strain (GLS), and measurements of left ventricular ejection fraction (LVEF), at baseline and following completion of adjuvant chemotherapy;
- cardiac troponin I release during adjuvant chemotherapy and one month after the last dose of epirubicin;
- adherence to enalapril;
- adverse reactions to enalapril;
- adverse events;
- any anxiety or distress related to trial participation.
- cancer and chemotherapy outcomes in the population under study

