### **11.5. Randomisation**

Randomisation will be performed using a minimisation scheme to ensure patients randomised to each group are comparable at baseline. The minimisation scheme will account for a planned 6 cycle adjuvant chemotherapy regimen (Epirubicin and Cyclophosphamide (EC) or Fluorouracil, Epirubicin and Cyclophosphamide (FEC)), and HER2 (human epidermal growth factor receptor 2) status (positive or negative).

Eligible patients will be randomised by delegated and trained members of the research team at each centre using a 24-hour, central, secure, web-based randomisation system with concealed allocation.

Eligible patients will be randomised in a 1:1 ratio to receive standard care plus enalapril maleate (intervention under study) or standard care (control arm/standard care).

Randomisation system web address:

<https://www.sealedenvelope.com/access/>

This system is available 24 hours a day, 7 days a week.

In the event that the randomisation system is not accessible, the team should contact NCTU staff in normal working hours:

Email: [[contact]](mailto:[contact])

[contact]

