- f) A Transthoracic Echocardiogram (TTE) must be performed at baseline. At the time of the TTE, blood pressure and heart rate should be measured, and recorded. A TTE will also be performed following the end of chemotherapy. Patients planned to receive Herceptin, must have their TTE performed prior to starting this. All TTEs must be transferred to the Core laboratory for analysis as part of the trial.
- g) Four weeks following the last dose of epirubicin.

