#### **13.2.12. Echocardiogram**

Cardiac function will be assessed via transthoracic echocardiography (TTE) at baseline, and 4 weeks following the last epirubicin dose.

All echocardiograms will be assessed by a Core Laboratory, led by [name], and [name] at The James Cook University Hospital. Images will be transferred from the study centre to the Core laboratory in accordance to the PROACT Echocardiogram Manual. [name], [name], and their team, will be blinded to the arm of the study to which patients are allocated.

Local reporting of the TTEs will be as per local hospital practice; the data reported by the Core laboratory (including GLS and LVEF) will be recorded in the eCRF and will be analysed as part of the secondary outcomes for the trial.

The PROACT Echocardiogram Manual provides further guidance to all centres involved in the study, detailing the number, quality and types of images to be acquired, and details of how to send these to the Core Laboratory. Heart rate and sinus rhythm will also be recorded at the time of the echocardiograms.

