### 17.1. Statistical Analysis

Data cleaning and analysis will be provided by staff within NCTU and Durham University. Primary analysis will follow intention to treat principles with patient data analysed according to randomisation and irrespective of intervention received; other analysis groups such as per-protocol may be considered subsequently. Every effort will be made to retain and include all patients who are part of the trial.

A full statistical analysis plan (SAP) will be developed for the outcome measures and agreed with the IDMEC and Chief Investigator prior to any analysis being undertaken.

Outcome data will be analysed at the end of the study, no interim analyses is planned.

The primary analysis of presence or absence of cardiac troponin T will be assessed using Fisher's exact test. Analysis of the secondary endpoints will be dependent upon the nature of the specific endpoint and data structure; global longitudinal strain (GLS) and left ventricular ejection fraction (LVEF) will be analysed as a change from baseline using a t-test to compare intervention and control groups.

Cardiac troponin I data will also be analysed using Fisher's exact test. Changes in cardiac troponin T and I will also be analysed as a continuous variable. Additional analysis of the primary endpoint will be performed using logistic regression to account for baseline factors (regimen and HER2 status). Adverse events data will be analysed using cross-tabulation. Sensitivity analysis will also be performed for adherence to the protocol.

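### GLS and LVEF are compared by a t-test on change from baseline; regressing follow-up on the baseline value would usually give tighter intervals at almost no cost

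*Combined protocol and SAP*

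**What the plan says.** Section 17.1 (Statistical Analysis) opens its account of the secondary outcomes in general terms: "Analysis of the secondary endpoints will be dependent upon the nature of the specific endpoint and data structure". The same sentence then names a method for the two echocardiographic measures: GLS and LVEF "will be analysed as a change from baseline using a t-test to compare intervention and control groups". No other section adjusts either measure for its baseline value. The only covariate-adjusted model is a logistic regression for the primary troponin T endpoint, with regimen and HER2 status as covariates.

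The section also promises more detail: "A full statistical analysis plan (SAP) will be developed for the outcome measures and agreed with the IDMEC and Chief Investigator", before any analysis is done. The combined document contains no further SAP text on GLS or LVEF.

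The baseline value is available. Section 13.2.12 schedules a scan at baseline and another four weeks after the last epirubicin dose, and states that "the data reported by the Core laboratory (including GLS and LVEF) will be recorded in the eCRF". Note f to the table in section 13.1 adds: "All TTEs must be transferred to the Core laboratory for analysis as part of the trial".

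**The concern.** Subtracting the baseline value amounts to assuming that follow-up rises one-for-one with baseline. Measurement error in the baseline value pulls the slope below 1, and section 7.2 itself describes LVEF as observer dependent. When the slope is not 1, the change score carries avoidable variance and the interval for the between-arm difference is wider than the data require.

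The trial was sized for troponin T only, and no power is stated for GLS or LVEF, so their precision depends on how they are analysed. Minimisation (section 11.5) balances regimen and HER2 status but not baseline GLS or LVEF. What is at stake is interval width and power on two secondary outcomes. There is no bias or type I error problem.

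**Working it through.** **The plan's own figure.** The only sample size is in section 17.1 (Sample Size): 140 patients for troponin T (47% against 20%, two-sided 5%, 90% power), raised to 170 for attrition. It reproduces. The continuity-corrected two-proportion formula gives 70 per arm, and exact enumeration of the two-sided Fisher test gives 90.8% power at 70 per arm. The figure of 140 is borrowed below as the number of evaluable scan pairs.

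**Inputs.** From the documents: 1:1 allocation, with one baseline and one follow-up scan per patient. Assumed, because the documents are silent: ρ, the correlation between baseline and follow-up, and k, the follow-up SD divided by the baseline SD.

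**Formulas**, in units of the baseline variance:

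- t-test on change: k² + 1 − 2kρ
- regression on baseline: k²(1 − ρ²)
- difference: (1 − kρ)²

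The difference is never negative. It is zero only when the slope kρ equals 1. Because allocation is 1:1, the large-sample result also holds if the slope differs between arms.

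Worked cells:

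- k = 1.0, ρ = 0.3: 0.91 / 1.40 = 0.650
- k = 1.3, ρ = 0.8: 0.6084 / 0.61 = 0.997

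**Variance ratio, regression to change score:**

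| k | ρ = 0.3 | ρ = 0.5 | ρ = 0.7 | ρ = 0.8 |
|---|---|---|---|---|
| 0.8 | 0.502 | 0.571 | 0.628 | 0.640 |
| 1.0 | 0.650 | 0.750 | 0.850 | 0.900 |
| 1.2 | 0.762 | 0.871 | 0.966 | 0.997 |
| 1.3 | 0.805 | 0.912 | 0.991 | 0.997 |

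With equal SDs (k = 1.0), regression would match the precision of 140 change scores with 140 × 0.65 = 91, 140 × 0.75 = 105, 140 × 0.85 = 119 or 140 × 0.90 = 126 patients.

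**Cost of estimating the slope.** The variance rises by a factor of about 1 + 1/(N − 4), which is 137/136 at N = 140. The square root is 1.004, or about 0.4% of interval width. The lost degree of freedom itself moves the critical t only from 1.9773 to 1.9774.

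**Net narrowing of the 95% CI at 140 pairs** (negative means wider), from simulation under no effect with 3000 runs per cell; it agrees closely with the formulas:

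| k | ρ = 0.3 | ρ = 0.5 | ρ = 0.7 | ρ = 0.8 |
|---|---|---|---|---|
| 0.8 | 29% | 24% | 20% | 20% |
| 1.0 | 19% | 13% | 7% | 5% |
| 1.2 | 12% | 6% | 1.3% | −0.2% |
| 1.3 | 10% | 4% | 0.1% | −0.2% |

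The worst cell is 0.4% wider at 100 pairs and 0.2% wider at 170. Adding regimen and HER2 status, if they explain nothing, costs a further 0.5 to 0.8 percentage points at 140 pairs (three covariates: √(137/134) = 1.011), so the worst case is about 1% wider.

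**Validity.** Simulated type I error was 0.044 to 0.059 for the t-test and 0.044 to 0.060 for regression (nominal 0.05, Monte Carlo SE 0.004). Mean estimates were within 0.008 baseline SD of zero for both methods.

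**Second check.** A separate simulation with 20,000 replicates at 70 per arm and equal SDs gave variance ratios of 0.66, 0.75, 0.86 and 0.95 at ρ = 0.3, 0.5, 0.7 and 0.9. With the slope set to exactly 1, it gave 1.006 to 1.008.

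**The case against.** The strongest reply is that nothing is wrong: a t-test on change is a valid, pre-specified analysis, and section 17.1 leaves the detail to a SAP still to be agreed. That is fair and it limits the severity. It does not remove the point, because the t-test is the only method named for these two outcomes and nothing in the text replaces it.

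The second reply is that the gain is unknown and may be trivial. This stands. For LVEF there is reason to doubt the k = 0.8 row: section 10.2 excludes LVEF below 50%, which restricts the baseline spread, while section 7.1 reports left ventricular systolic dysfunction in 9.7% of patients within 12 months, which could widen the follow-up spread. At k of 1.2 to 1.3 and ρ of 0.7 to 0.8, the two methods are practically equal. On the other side, measurement error lowers ρ, and k = 1.0 still gives 5% to 19%. The range quoted in the conclusion therefore leaves out the k = 0.8 row.

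Third, the figure of 140 belongs to troponin T. Section 10.2 accepts that absolute LVEF measurement may not be possible in every patient, so there may be fewer usable pairs. The result at 100 pairs shows that this changes little.

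**Conclusion.** The point holds as a low-priority improvement, not as an error in the plan. Regression on the baseline value is never less precise than the change score in large samples. At 140 pairs its worst-case cost is about 0.4% of interval width. For k between 1.0 and 1.3 and ρ between 0.3 and 0.8, the effect runs from about 19% narrower to about 0.2% wider. These values of k and ρ, and the 140 pairs, are assumptions; the size of the gain in this trial cannot be settled from the documents. The primary analysis and the 140/170 sample size are untouched.

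**What to change.** In the SAP, before any analysis, define the main analysis of GLS and of LVEF as a linear regression of the follow-up core-laboratory value on arm and the baseline core-laboratory value of the same measure. Report the adjusted mean difference with a 95% CI. Keep the t-test on change as a sensitivity analysis. Regimen and HER2 status may be added for consistency with the adjusted troponin T model, but no precision gain is claimed for them.

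The change costs SAP wording and one estimated coefficient. It needs no new data or visits, and no patient is lost, because both methods use the same pair of scans.

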## 9. Trial Design

### 9.1. Summary

A prospective, randomised, open-label, blinded end-point, superiority trial in patients undergoing anthracycline-based adjuvant chemotherapy for breast cancer. Patients will be randomised in a 1:1 ratio to enalapril (intervention) or control (standard care). The trial will evaluate the effectiveness of enalapril in preventing cardiotoxicity detected by cardiac troponin T.

The trial is anticipated to take 30 months to complete and will randomise 170 patients due to receive anthracycline-based adjuvant chemotherapy for their breast cancer at participating NHS Trusts.

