### 10.2. Exclusion Criteria

- Positive baseline cardiac troponin T ( $\geq 14\text{ng/L}$ );
- known contraindication to ACE inhibitor e.g. renal artery stenosis, severe aortic stenosis;
- are taking, or have a previous intolerance to ACEI (e.g. angioedema);
- patient already taking other agents acting on the renin-angiotensin-aldosterone system e.g. Aliskiren, angiotensin receptor blockers (ARBs), Entresto (sacubitril/valsartan), spironolactone, eplerenone;
- LVEF  $<50\%$ \*;
- estimated GFR  $< 30\text{ mL/min/1.73m}^2$  at baseline;
- hyperkalaemia defined as serum potassium  $\geq 5.5\text{mmol/L}$ ;
- symptomatic hypotension, or Systolic Blood Pressure  $<100\text{mmHg}$ ;
- poorly-controlled hypertension (Blood Pressure  $>160/100\text{mmHg}$ \*\*, or ambulatory BP of  $150/95\text{mmHg}$ );
- previous myocardial infarction;
- known metastatic breast cancer;
- previous exposure to anthracycline chemotherapy;
- are pregnant or breastfeeding
- Previous Herceptin treatment or planned Herceptin treatment within four weeks following anthracycline chemotherapy
- for patients of childbearing potential: refusal to use adequate contraception throughout the trial;\*\*\*
- any other cancer diagnosis;
- participation in other interventional medicinal trials in the past 6 months;
- judgment by the Investigator that the patient should not participate in the study, for example, if the patient is unlikely to comply with study procedures, restrictions, and requirements.

\*<50% as defined by Simpson's biplane method; if absolute measurements are not possible, then a visually normal assessment of LVEF is acceptable for inclusion.

\*\*White coat hypertension is more common, and should be ruled out by an ambulatory blood pressure monitor

\*\*\*Female patients between the ages of 18 and 50 will receive a pregnancy test at baseline.

Adequate methods of contraception are those that can achieve a failure rate of less than 1% per year when used consistently and correctly, such methods include:

- combined (estrogen and progestogen containing) hormonal contraception associated with inhibition of ovulation
  - oral
  - intravaginal
  - transdermal
- progestogen-only hormonal contraception associated with inhibition of ovulation
  - oral
  - injectable
  - implantable
- intrauterine device (IUD)
- intrauterine hormone-releasing system (IUS)
- bilateral tubal occlusion
- vasectomy/vasectomised partner

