#### **Eligibility blood sample**

At baseline, up to 5mL of blood will be taken in a serum-separation tube (SST) for the troponin T eligibility check. This blood sample will be collected and sent for immediate local processing. If the local processing laboratory finds that the sample collected is haemolysed, a repeat sample will be requested immediately. Serum from this sample will be sent for central analysis at Newcastle Laboratories (Newcastle-upon-Tyne Hospitals NHS Foundation Trust). If the serum sample is not sent on the same day, it will be frozen and transported the following day at -20°C. This baseline serum sample will be received and analysed in real time for Troponin T. The laboratory will confirm the Troponin T result with the site team and this will be recorded in the eCRF. An aliquot of serum from this baseline sample will be stored at -80°C for troponin I analysis at the end of the study.

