## 17. Statistics

### 17.1. Sample Size

Audit data from 36 patients and 143 samples, showed a positive troponin T in 47% of patients who received  $>300\text{mg/m}^2$  of anthracycline in a six-cycle regimen. As a sensitive marker of cardiac cell death, we expect troponin to be “turned off” if enalapril is effective. There are other potential causes of an elevated troponin during chemotherapy that are accounted for in the sample size calculation. There is clinical consensus that a rate of 20% in elevated troponin would fully account for other causes such as infection.

Assuming alpha of 5%, and 90% power, 140 patients are needed to detect a reduction in the proportion of patients with cardiac troponin T present from 47% to 20% using a two-sided Fisher's exact test.

There is consensus within the clinical community that, a large effect size will be necessary to convince the clinical community to change the pathway of care for these patients.

Allowing for attrition, the trial will recruit and randomise 170 patients.

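### The binary troponin I analysis makes no use of baseline troponin I, so persistent pre-treatment elevation can be scored as release and weaken this secondary comparison

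*Combined protocol and SAP*

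**What the plan says.** **Entry.** Section 10.2 lists "Positive baseline cardiac troponin T" (14 ng/L or more) as an exclusion, and footnote d to the schedule in section 13.1 confirms that baseline troponin T decides eligibility. Troponin I has no counterpart. Section 13.2.8 (Eligibility blood sample) says: "An aliquot of serum from this baseline sample will be stored at -80°C for troponin I analysis at the end of the study". A raised baseline troponin I therefore cannot affect entry.

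**Outcome.** The synopsis describes troponin I release at any time during adjuvant chemotherapy and one month after the last epirubicin dose. Section 9.3 says much the same without the words for any time. Neither gives a cut-off or refers to baseline. Section 9.2 does give a cut-off for troponin T.

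**Sampling.** The endpoint samples are drawn before cycles 2 to 6 and one month after the last epirubicin dose (section 13.2.8, Blinded end-point blood samples). The baseline sample is separate.

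**Analysis.** The Statistical Analysis section says "Cardiac troponin I data will also be analysed using Fisher's exact test", with no restriction or adjustment for baseline. The next sentence adds a continuous analysis of changes in troponin T and I. The logistic model covers the primary endpoint only and adjusts for regimen and HER2 status. GLS and LVEF, by contrast, are explicitly analysed as change from baseline. A full SAP is promised before any analysis; it is not among the documents available here.

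**The concern.** Because of the entry criterion, a positive troponin T during treatment is a new positive. The same cannot be said of troponin I. If a patient enters with raised troponin I that persists, and release is scored by a threshold, that patient is an event whichever arm they are in. Such events say nothing about epirubicin or enalapril. They add equally to both arms in expectation and shrink the difference between them.

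The protocol treats troponin T and I as markers of the same early process (section 7.2), so readers will look to troponin I to see whether it agrees with the primary result. With baseline positives removed for one marker and not the other, the two binary results would answer slightly different questions. A failure of troponin I to agree could then partly reflect how events were counted.

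Supplying a cut-off alone would not settle this. A patient above the cut-off at baseline and afterwards would still be counted.

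**Working it through.** **1. Reproduce the plan's own figure.** The Sample Size section states "Assuming alpha of 5%, and 90% power, 140 patients are needed to detect a reduction" in troponin T positivity from 47% to 20%, "using a two-sided Fisher's exact test". Allocation is 1:1 (section 9.1).

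Pooled-variance formula, d = 0.47 − 0.20 = 0.27, mean proportion 0.335:

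n = [1.960·√(2 × 0.335 × 0.665) + 1.2816·√(0.47 × 0.53 + 0.20 × 0.80)]² / 0.27² = (1.308 + 0.820)² / 0.0729 ≈ 62.1, so 63 per arm uncorrected.

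With continuity correction: n′ = (n/4)·[1 + √(1 + 4/(n·d))]² = (62.1/4) × [1 + √(1 + 4/16.77)]² ≈ 69.3, so 70 per arm, 140 in total. The stated figure reproduces. Full enumeration of the two-sided Fisher test gives power of 90.8% at 70 per arm and 95.4% at the 85 per arm randomised. The step from 140 to 170 implies attrition of 1 − 140/170 = 17.6%.

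**2. Inputs for troponin I.** The documents give no troponin I event rate and no baseline prevalence. Two assumptions are therefore needed:
- new-positivity rates of 47% and 20%, borrowed from troponin T;
- a share b of patients who are troponin I positive at baseline and stay positive in both arms. A range is shown.

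**3. Model.** If these patients are counted as events, each arm's rate becomes p = b + (1 − b)·p₀, and the difference becomes (1 − b) × 27 points. For b = 10%: control 0.10 + 0.90 × 0.47 = 52.3%; enalapril 0.10 + 0.90 × 0.20 = 28.0%; difference 24.3 points. If they are removed, the rates return to 47% v 20% with about 70(1 − b) per arm.

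**4. Results (exact two-sided Fisher power).**

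| b | Control v enalapril | Difference (points) | Odds ratio | Power, counted, 70/arm | Power, removed (n/arm) | Power, counted, 85/arm |
|---|---|---|---|---|---|---|
| 0% | 47.0% v 20.0% | 27.0 | 0.28 | 90.8% | 90.8% (70) | 95.4% |
| 2% | 48.1% v 21.6% | 26.5 | 0.30 | 88.8% | 90.3% (69) | 94.1% |
| 5% | 49.7% v 24.0% | 25.7 | 0.32 | 85.5% | 89.0% (66) | 91.8% |
| 10% | 52.3% v 28.0% | 24.3 | 0.36 | 79.5% | 87.2% (63) | 87.7% |
| 20% | 57.6% v 36.0% | 21.6 | 0.41 | 67.7% | 82.8% (56) | 77.9% |

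At 70 per arm, removal recovers 90.3 − 88.8 = 1.5 points at b = 2%, 89.0 − 85.5 = 3.5 points at 5%, and 87.2 − 79.5 = 7.7 points at 10%. If some baseline positives revert to negative, the dilution is smaller while restriction still removes the same patients, so the gain shrinks.

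**The case against.** A reader might infer that the plan counts every positive troponin I sample as release, and so counts the wrong events. The documents do not support that. They give no event rule for troponin I at all, and release during chemotherapy could equally be read as new release. The threshold reading rests on the parallel with troponin T and the synopsis wording for any time. This objection stands, which is why the point is conditional.

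Nor would every baseline positive be scored. The baseline sample lies outside the endpoint window, so a transient elevation that has gone by cycle 2 would not count.

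The prevalence may also be low. Entry already excludes raised troponin T, previous myocardial infarction, LVEF below 50% and eGFR below 30, which probably removes some troponin I positives. At b = 2% the effect is slight, and with all 85 per arm analysed power stays above 90% even at 5%. The protocol makes no power claim for troponin I.

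Two parts of the plan soften the gap: the continuous analysis of change in troponin I, and the deferred SAP. The first presumably uses the baseline value, but it is a separate analysis and does not correct the binary one. The second is where the rule belongs, but nothing available shows that it was set there. The 20% allowance in the Sample Size section does not help either: it concerns troponin T and causes arising during chemotherapy.

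**Conclusion.** The point holds in conditional form. As written, the binary troponin I analysis ignores baseline troponin I. If release is scored by a cut-off, elevation that predates epirubicin and persists to cycle 2 or later can be counted as release.

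The consequence is attenuation of one secondary comparison. It would be wrong to infer a bias in favour of enalapril, since randomisation balances baseline positives in expectation. It would also be wrong to infer a threat to the primary result, since the troponin T analysis is unaffected.

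The size cannot be determined from the documents. The illustrative loss against 90.8% is 2.0 points at b = 2%, 5.3 at 5% and 11.3 at 10%, only part of which removal recovers. These figures depend wholly on an assumed b, on rates borrowed from troponin T, on persistence in both arms, and on 70 analysed per arm.

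**What to change.** Before the troponin I batch assay, state in the SAP:

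- the troponin I cut-off for the assay used;
- release as new positivity: baseline aliquot below the cut-off and at least one post-baseline sample at or above it;
- Fisher's exact test in baseline-negative patients. The baseline sample precedes randomisation and the batch assay is blinded, so this restriction keeps the randomised comparison intact;
- a supporting logistic model in all patients with a baseline result, adjusting for baseline troponin I, regimen and HER2 status. Its outcome should be any post-baseline sample at or above the cut-off, since new positivity is not defined for baseline positives. Baseline troponin I is best entered as the measured value, because a positive/negative indicator would predict perfectly if every baseline positive stayed positive;
- the number of baseline positives and of missing baseline results, by arm.

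The cost is SAP wording. The aliquot is already to be stored and assayed, so no extra samples, visits or patients are needed. The small downside is that patients who are baseline-positive or have no usable baseline troponin I result leave the Fisher comparison; the model retains the former.
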